## **6. CONDUCT OF THE STUDY**

### **6.1. Regulatory and ethical considerations, including the informed consent process**

The study will be conducted in accordance with all applicable regulatory requirements.

The study will be conducted in accordance with the International Conference on Harmonization (ICH) Guideline for Good Clinical Practice (GCP), all applicable subject privacy requirements and the guiding principles of the Declaration of Helsinki.

GSK will obtain favorable opinion/approval to conduct the study from the appropriate regulatory agency, in accordance with applicable regulatory requirements, prior to a site initiating the study in that country.

Conduct of the study includes, but is not limited to, the following:

- Institutional Review Board (IRB)/Independent Ethics Committee (IEC) review and favorable opinion/approval of study protocol and any subsequent amendments.
- Subject informed consent.
- Investigator reporting requirements as stated in the protocol.

GSK will provide full details of the above procedures to the investigator, either verbally, in writing, or both.

Freely given and written or witnessed/thumb printed informed consent must be obtained from each subject prior to participation in the study.

GSK Biologicals will prepare a model Informed Consent Form (ICF) which will embody the ICH GCP and GSK Biologicals required elements. While it is strongly recommended that this model ICF is to be followed as closely as possible, the informed consent requirements given in this document are not intended to pre-empt any local regulations which require additional information to be disclosed for informed consent to be legally effective. Clinical judgement, local regulations and requirements should guide the final structure and content of the local version of the ICF.

The investigator has the final responsibility for the final presentation of the ICF, respecting the mandatory requirements of local regulations. The ICF generated by the investigator with the assistance of the sponsor's representative must be acceptable to GSK Biologicals and be approved (along with the protocol and any other necessary documentation) by the IRB/IEC.

## **6.2. Subject identification and randomisation**

### **6.2.1. Subject identification**

Subject identification numbers will be the same as the ones assigned in the primary study MALARIA-092, with the exception that the identifying protocol number will be changed to reflect the new study, as applicable. New identification numbers will be generated for infectivity controls.

### **6.2.2. Randomization of treatment**

#### **6.2.2.1. Randomization of supplies**

The list of treatment numbers for the supplies is generated at GSK Biologicals, using MATerial EXcellence (MATEX), a program developed for use in Statistical Analysis System (SAS) (Cary, NC, USA) by GSK Biologicals.

#### **6.2.2.2. Treatment allocation to the subject**

The treatment numbers will be allocated by dose. The allocation will be sequential in the order in which the subjects are vaccinated.

##### **6.2.2.2.1. Study group and treatment number allocation**

The target is to enroll all subjects who were vaccinated and have undergone challenge in the MALARIA-092 study and who are willing to take part in this MALARIA-102 booster study. A minimum of 40 subjects (20/vaccine group) are expected to be enrolled in this study. However there may be more or fewer subjects who consent to join the study.

Subjects from the MALARIA-092 study will not be randomized but the treatment allocation will be done via a randomization system on internet (SBIR) to allow monitoring of vaccine storage and expiry dates.

Subjects from the infectivity control group will not be randomized and will not appear in SBIR; they will simply be registered in the eCRF database.

After obtaining the signed and dated ICF from the subject and having checked the eligibility of the subject, the study staff in charge of the vaccine administration will access SBIR. Upon providing the subject identification number, the randomisation system will provide the treatment number to be used for the dose.

The number of each administered treatment must be recorded in the eCRF on the Vaccine Administration screen.

When SBIR is not available, please refer to the SBIR user guide or the Study Procedures Manual (SPM) for specific instructions.

### **6.3. Method of blinding**

This study is open-label.

The laboratory in charge of the laboratory testing will be blinded to the treatment, and codes will be used to link the subject and study (without any link to the treatment attributed to the subject) to each sample.

### **6.4. General study aspects**

Supplementary study conduct information not mandated to be present in this protocol is provided in the accompanying SPM. The SPM provides the investigator and the site personnel with administrative and detailed technical information that does not impact the safety of the subjects.

#### **6.4.1. Mosquito challenge**

Subjects from the two vaccine groups (P-Fx and NP-Fx) completing their immunization course will be challenged with sporozoite-infected mosquitoes to determine whether the expected protective response has developed. Such challenges are mandated by the absence of any laboratory tests that will unequivocally predict protection. The challenge is scheduled to occur approximately three weeks after vaccination (Day 22 [Visit 3]).

Unimmunized infectivity control subjects will also be challenged to verify the adequacy of the challenge.

Subjects undergoing malaria challenge will receive an emergency notification card that outlines their participation in the study with details on the exposure to malaria, as well as the appropriate investigator contact telephone numbers. Details of this information may vary, depending on the venue selected for the hotel phase of the study.

##### **6.4.1.1. Contraindications to malaria challenge**

The only absolute contraindication to mosquito challenge is pregnancy. If this occurs after immunization but before undergoing challenge, the subject must not be challenged and she will be followed for the duration of the study or pregnancy whichever is longer.

A subject with a minor illness but who does not have fever during the pre-challenge assessment may be challenged at the discretion of the investigator. If the subject is

moderately to severely ill with fever on the day of the challenge, he/she will not be challenged. Challenge can be performed within the time window defined in [Table 6](#) and [Table 7](#), at the discretion of the investigator if the subject becomes well. Subjects who will not be challenged will be followed for the duration of the study.

Any conditions which according to the judgment of the investigator would make the challenge unsafe.

#### **6.4.1.2. Parasite and mosquito strains**

The 3D7 clone of *P. falciparum* is a human malaria isolate that has never been passed through monkeys, is well-adapted to culture, is a good producer of gametocytes that can infect mosquitoes, is susceptible to currently available, approved, anti-malarial compounds, and has previously been used in the WRAIR challenge model to successfully infect human subjects under a Biologics Master File submitted to the Food and Drug Administration (FDA). Master seed lots of these parasites have been developed and stored at WRAIR. All blood products used for malaria and mosquito culturing will be commercially tested for HIV, HBsAg, HCV, and syphilis. The mosquitoes used will be laboratory-born and reared *Anopheles stephensi*.

#### **6.4.1.3. Infection of human subjects**

Mosquitoes infected approximately 2-3 weeks earlier that are likely to contain sporozoites in their salivary glands will be allowed to feed on the subjects. For each subject, five mosquitoes will be allowed to feed over five minutes, after which they will be dissected to confirm how many were infected, and the salivary glands scored. If required, additional mosquitoes will be allowed to feed until a total of five infected mosquitoes with a minimum 2+ salivary glands score have fed [[Wirtz, 1987](#)]. The mosquito feedings will be performed in a secure insectary of the Department of entomology at WRAIR. Subjects will be observed for at least 30 minutes following completion of the sporozoite challenge in order to assess them for any evidence of acute allergic reactions related to mosquito exposure. To date, no severe allergic reactions related to mosquito bites have been documented in the context of the WRAIR malaria challenge model. Routinely, transient local allergic reactions (itching, rash) typical of mosquito bites occur at sites of the bites.

#### **6.4.1.4. Determining parasitemia**

Post-challenge, parasitemia will be determined by microscopy of Giemsa-stained thick blood films (smear) and PCR. Microscopy will be performed on thick smears using a validated Standard Operation Procedure.

All blood films (positive and negative) will be archived at the study centers for later re-examination and confirmation, if required.

#### **6.4.1.5. Management of infected human subjects**

The pre-patent period (period between infection with a parasite and the demonstration of the parasite in the body) for *P. falciparum* in man normally averages 9-12 days. In

previous studies, the pre-patent period in controls varied from 7-18 days. The shortest reported pre-patent period in man is 5 days, and the longest is 25 days [Ballou, 1987]. An immunized individual who does not have complete protection may have a prolongation of the parasite pre-patent period.

Beginning on the fifth day after their challenge (Day 27 [Visit 4]), subjects will be seen and evaluated daily by a study investigator and blood will be drawn for blood smears and PCR to check for the presence of parasites as described in Section 6.4.1.4. If fever or symptoms develop at any time, blood smears will be done more frequently (every 6 to 12 hours), and a study investigator will evaluate the subject. A confirmed positive result will be relayed immediately to the on-call investigator/study personnel by the microscopists. The infection will be treated early (i.e., as soon as parasites can be identified on thick smear) according to the treatment regimen outlined in Section 6.4.1.6. Additional PCR tests may also be performed at investigator discretion, but may not necessarily be run in real time.

Beginning on the ninth day post-challenge (Day 31 [Visit 8]), a group of hotel rooms in the local area of WRAIR will be reserved for malaria-challenged subjects. Subjects will be required to spend their nights there to allow for more rapid assessment of any potential symptoms of malaria during the hours that the study centers are closed. There will be an investigator present on-site and available for subject assessment. There will also be qualified study personnel on site 24 hours per day during the hotel phase of the study.

During the hotel phase, all challenged subjects will be assessed on a daily basis in an identical manner. An evaluation will be done ideally each morning (headache, muscle aches, etc.) and blood will be drawn for smear and PCR. There may be the rare occasion where subject assessment is done later in the day but every effort must be made for the assessment to be done in the morning. All challenged subjects will be instructed to check in with clinical staff by telephone call or texting or in-person each afternoon or evening during the hotel stay until they are positive for malaria. A member of the WRAIR staff will contact him/her and if they are not available during the time of contact. A telephone script will be used to guide the site staff during these contacts. They will be asked if they feel any differently since they were seen in the morning. At any time required, the on-duty investigator will arrange for the timely production of blood smears and PCR, along with their examination and interpretation, in order to treat rapidly those subjects in whom therapy for malaria is indicated. Once a positive smear is identified, daily blood films will continue to be obtained until three consecutive films are negative (separated by more than 12 hours). A complete blood count and serum chemistry tests will be done when parasites are initially found in the blood (this could be done on the day of parasitemia detection or the day after).

The maximum hotel stay for malaria-challenged subjects should be approximately 10 nights (between Day 31 [Visit 8] to Day 40 [Visit 17], inclusive). A subject who develops malaria, is treated, and has three consecutive negative malaria smears (separated by more than 12 hours), will not need to remain in the hotel. The investigators will be responsible for accounting for any subjects who do not arrive in the hotel during the challenge phase. If required, the investigators will physically locate and treat any malaria-infected subject who is unable to maintain the follow-up dictated by this study.

If infection does not develop within 18 days, the subject will be released from staying nightly at the hotel. Subjects who do not develop malaria will be required to come to the clinical center for evaluation and blood drawing for smears and PCR every two days up to 28 days post-challenge (Days 42 [Visit 18], 44 [Visit 19], 46 [Visit 20], 48 [Visit 21] and 50 [Visit 22]). Exceptionally this can occur within 1 or 3 days if the subject cannot make the visit or for schedule conflicts. A subject who develops malaria and has three consecutive (separated by more than 12 hours) negative smears following initial treatment may be excused from the remaining hotel visits and the late post-challenge clinic visits at Days 42, 44, 46 and 48 (20, 22, 24 and 26 days post-challenge), but will be required to come to the clinic center at Day 50 (28 days post-challenge [Visit 22]).

Telephone contact (spoken or written) will be made if the subject does not keep a scheduled follow-up appointment. Symptom screening via telephone may suffice in lieu of clinical visits for Days 42, 44, 46 and 48 which fall upon a weekend.

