**Table 3** **Blinding of study epochs**

Study Epochs	Blinding
Epoch 001	Open
Epoch 002	Open
Epoch 003	Open
Epoch 004	Open

- **Sampling schedule:**

For subjects from the P-Fx and NP-Fx groups:

- Blood samples for assessment of anti-CS and anti-HBs immune response and for serum repository will be collected at screening, Day 1\*, on the day of challenge (Day 22), 28 days post-challenge (Day 50) and at study end (Day 190).
- Blood samples for peripheral blood mononuclear cells (PBMCs) and plasma repository will be collected at screening, Day 1\*, 7 days post-booster (Day 8), on the day of challenge (Day 22), 28 days post-challenge (Day 50) and at study end (Day 190).

\*Before vaccine administration. These samples might not be drawn if Visit 1 occurs less than one week after screening, at the discretion of the investigator.

For all subjects:

- Blood samples for the evaluation of biochemistry (alanine aminotransferase [ALT], aspartate aminotransferase [AST], creatinine) and hematology (hemoglobin, leukocytes [white blood cells; WBC], platelets) parameters will be collected at screening, Day 1\*, 7 days post-booster\* (Day 8), Day 22, the day of first parasitemia and 28 days post-challenge (Day 50). Following a bleeding procedure failure or laboratory failure, repeat bleeds can be considered upon investigator discretion no more than three times, or if medically indicated for full investigation of a potential adverse event or clarification of subject eligibility.

\*Not applicable for the infectivity controls.

- Blood sample for assessment of parasitemia (blood smear and PCR) will be collected daily for 14 days (from Day 27 [Visit 4] to Day 40 [Visit 17]) and then every two days for nine days (Day 42 [Visit 18], Day 44 [Visit 19], Day 46 [Visit 20], Day 48 [Visit 21] and Day 50 [Visit 22]). Exceptionally this can occur within 1 or 3 days if the subject cannot make the visit or for schedule conflicts. For subjects who develop malaria, blood smear and PCR may be discontinued once the subject has three consecutive negative smears (separated by more than 12 hours) following the initial treatment.

- Blood samples for testing of HIV, hepatitis C virus (HCV) and HBsAg will be collected from all subjects at screening.
- Urinary pregnancy test (urine beta-human chorionic gonadotropin [ $\beta$ -HCG]) will be performed on all women at screening, at Day 1\* and on the day of challenge (Day 22).

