## 4. CASE DEFINITION

The following will be used as case definition of *P. falciparum* infection:

- Asexual blood stage *P. falciparum* parasite density  $> 0$  detected by blood slide reading.

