5.3. Efficacy

5.3.1. Analysis of efficacy planned in the protocol

The analysis of efficacy will be performed on the PPS for analysis of immunogenicity and efficacy.

Efficacy will be assessed by comparison of *P. falciparum* parasitemia incidence and time-to-onset of *P. falciparum* parasitemia after sporozoite challenge. The analysis of the primary objective will be based on blood smears results; additional exploratory analyses will be performed based on PCR results (tertiary objectives).

Vaccine efficacy (VE) is defined as $100 * (1 - \text{Relative Risk})$. Relative risk of infection and 95% CI will be calculated.

Fisher's Exact test will be used for the comparison of *P. falciparum* parasitemia incidence after challenge between each one of the study groups (P-Fx and NP-Fx) and the infectivity control group.

Kaplan-Meier analysis will be performed on time-to-onset of *P. falciparum* parasitemia, for comparisons between each one of the study groups (P-Fx and NP-Fx) and the infectivity control group, using the log-rank statistic.

The same methodology will be applied for the evaluation of the study groups (P-Fx vs. NP-Fx) versus each other. If there are sufficient evaluable subjects (at least a 1:2 ratio between vaccinated and control groups) to draw some conclusions, descriptive analyses based on initial group assignment versus control will be performed.

All statistical tests will be two-tailed at 5% significance level.

Risk periods

For the analyses of time-to-onset of parasitemia (Kaplan-Meier and log-rank), time-at-risk will start on first day of challenge. Time-at-risk will be censored on Visit 22 (Day 50; 28 days post-challenge), drop-out date, start date of anti-malarial treatment or date meeting an endpoint, whichever occurs first. Time-at-risk will be calculated as: censor date – challenge date + 1.

For the analysis of proportion affected (relative risk), all subjects included in the PPS for analysis of immunogenicity and efficacy will be considered at risk of infection and no censoring or elimination will be applied for subjects not completing the entire protocol defined post-challenge follow-up (Day 50; 28 days post challenge).

Case definition

The following will be used as case definition of *P. falciparum* infection:

Asexual blood stage *P. falciparum* parasite density > 0 detected by blood slide reading (or PCR for tertiary objectives).

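### Protocol 6.4.1.5 lets a telephone symptom check replace a weekend visit on Days 42–48, which can drop at least one scheduled endpoint slide and PCR for any subject still negative at Day 40

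*Protocol*

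**What the plan says.** Protocol section 3 (sampling schedule) sets slides and PCR "daily for 14 days (from Day 27 [Visit 4] to Day 40 [Visit 17]) and then every two days for nine days", ending at Day 50. The synopsis, the footnotes to Tables 4 and 5, Tables 8 and 14, and SAP section 2 list the same days. The flexibility given for these visits is: "Exceptionally this can occur within 1 or 3 days if the subject cannot make the visit or for schedule conflicts". That rule moves a sample; it does not remove one.

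Section 6.4.1.5 repeats the requirement for subjects who do not develop malaria: they "will be required to come to the clinical center for evaluation and blood drawing for smears and PCR every two days" until 28 days post-challenge. Its next paragraph then adds the exception: "Symptom screening via telephone may suffice in lieu of clinical visits for Days 42, 44, 46 and 48 which fall upon a weekend". The exception is not limited to any study group and does not cover Day 50.

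A case depends on a laboratory reading. Protocol section 4 requires parasites "detected by blood slide reading", and SAP 5.3.1 has "parasite density > 0 detected by blood slide reading (or PCR for tertiary objectives".

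Subjects who have been treated and have three consecutive negative smears are already excused from Days 42 to 48. The telephone sentence therefore bears mainly on subjects who are still at risk of becoming a case.

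**The concern.** One rule requires an endpoint sample and the other allows a contact that cannot produce one. Section 3 forbids waivers except for immediate safety concerns and calls adherence to the section 6.5 procedures essential, so a site following the text could not tell which rule governs.

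The stake is endpoint ascertainment in the last third of follow-up. Section 6.4.1.5 gives a pre-patent range of 7–18 days in earlier controls and a longest reported period of 25 days, and says that an incompletely protected vaccinee may have prolonged pre-patency. Day 40 is 18 days post-challenge, so those still at risk afterwards should be mostly vaccinees. A slide lost in that window delays the recorded onset of a late breakthrough, and time-to-onset is the secondary efficacy endpoint.

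The SAP has no rule specific to a visit done by telephone. For the relative-risk analysis, Protocol 11.9 and SAP 5.3.1 keep every per-protocol subject at risk with no elimination for incomplete follow-up, so a slide not taken in effect counts as not positive. Elimination code 2090 (blood-sample schedule not followed) refers to SAP Table 1, which has no interval for Visits 18–21. It is therefore unclear whether a telephone visit affects membership of the per-protocol set.

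**Working it through.** **The plan's own schedule.** Days 27–40 give 40 − 27 + 1 = 14 daily slides. Days 42–50 span 50 − 42 + 1 = 9 days with 5 visits. The total is 14 + 5 = 19 slides, and the longest interval is 2 days. Challenge is on Day 22, so Day d is d − 22 days post-challenge; Days 42, 44, 46, 48 and 50 are 20, 22, 24, 26 and 28 days, as the protocol states.

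**Weekday enumeration.** Relative to the challenge weekday, Days 42, 44, 46 and 48 are shifted by 20, 22, 24 and 26 days, which is 6, 1, 3 and 5 days modulo 7. Removing each visit that falls on Saturday or Sunday gives:

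| Challenge weekday | Slides that can be lost | Resulting interval(s) | Slides left of 19 |
|---|---|---|---|
| Monday | Day 42 (Sun), Day 48 (Sat) | 40→44, 46→50 | 17 |
| Tuesday | Day 48 (Sun) | 46→50 | 18 |
| Wednesday | Day 46 (Sat) | 44→48 | 18 |
| Thursday | Day 46 (Sun) | 44→48 | 18 |
| Friday | Day 44 (Sat) | 42→46 | 18 |
| Saturday | Day 44 (Sun) | 42→46 | 18 |
| Sunday | Day 42 (Sat) | 40→44 | 18 |

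All seven weekdays can lose at least one slide, and the longest interval is 4 days in each case. The reason is simple: the visits fall on the 1st, 3rd, 5th and 7th of seven consecutive days, so any Saturday–Sunday pair contains at least one.

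**Delay in recorded onset.** Suppose the slide on day d is lost. An infection first patent after the slide on d − 2 and by day d would have been dated to d. Without symptoms it is now dated to d + 2, which is 2 days late. An infection first patent after d is dated as planned.

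**Does the window matter?** The longest pre-patent period the protocol cites, 25 days, corresponds to Day 22 + 25 = Day 47. That lies between Day 46 and Day 48.

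**Can the existing tolerance absorb the weekend?** Move a Saturday sample to Friday (d − 1) or a Sunday sample to Monday (d + 1). The neighbouring slides stay at d − 2 and d + 2, so the intervals become 1 and 3 days, or 3 and 1. For a Monday challenge the slides fall on Days 40, 43, 44, 46, 47 and 50, with intervals 3, 1, 2, 1 and 3. No visit is added and none falls on a weekend, but the longest interval is 3 days, not 2.

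**Illustration for the primary endpoint.** The documents give no count of infections that would be missed altogether, so this is an assumption. Take the planning case of 19/20 controls and 6/20 vaccinees positive: VE = 1 − (6/20)/(19/20) = 68.4%, Fisher p = 0.00004. If the true vaccinee count were 7 or 8, VE would be 63.2% (p = 0.0001) or 57.9% (p = 0.0004). Each infection missed altogether moves VE by 0.05/0.95 = 5.3 points, and significance does not change.

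**The case against.** The strongest reply is that the loss is narrow and partly covered.

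- **Four days unobserved.** A reader might infer this, but the documents do not support it. The telephone screen takes place in the middle of the interval, and section 6.4.1.5 has symptoms at any time trigger smears every 6 to 12 hours. Only symptom-free parasitemia can go unseen.
- **Infections never counted.** A reader might infer that the primary endpoint is materially biased. The Day 50 slide is outside the exception, so an untreated infection that persists can still be found then. Missing it altogether would need positivity confined to the skipped day, which no passage describes; the alternate-day schedule already accepts that risk on odd-numbered days.
- **Only vaccinees affected.** The rule applies to all groups, and controls challenged on the same day share the same weekend pattern. Those at risk after Day 40 are mostly vaccinees, but not only vaccinees.
- **14 of 20 per group affected.** At the planning efficacy, 14 of 20 is the number assumed to stay uninfected. They have no onset to misdate. The relevant number is breakthroughs first patent after day 18, which the documents do not give.
- **The documents are silent on missing slides.** Not quite: SAP 9.1.2.2 says missing laboratory results are not replaced. It does not say how onset is dated across a missing slide.

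It also stands that the option is permissive, that all analyses are declared descriptive (Protocol 11.12, SAP section 6), and that both vaccinated groups follow the same rule. None of this removes the conflict between the two paragraphs of 6.4.1.5, or the fact that the calendar makes the exception available to every subject still negative.

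**Conclusion.** The inconsistency is real and should be corrected, with a modest expected effect. If the telephone option is used, one of the four Day 42–48 slides can be lost for six of the seven challenge weekdays and two for a Monday challenge. The longest slide interval goes from 2 to 4 days, and symptom-free late parasitemia can be dated up to 2 days late.

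The results affected are the tail of the vaccinee Kaplan-Meier curves, time-to-onset, and the tertiary P-Fx versus NP-Fx and PCR comparisons. The binary primary endpoint and the log-rank test against controls should change little, because the Day 50 slide remains and control events are expected earlier. The size of either effect cannot be derived from the documents.

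This assumes that visits otherwise fall on their nominal days, that the option is used whenever it is available, and that the subject is still negative at the affected visit. A visit moved off the weekend under the existing tolerance loses no slide.

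**What to change.** **Protocol 6.4.1.5.** Reconcile the telephone sentence with the sampling schedule, so that the endpoint slide and PCR are still obtained for subjects at risk. The existing 1-or-3-day tolerance can accommodate weekends. This concerns endpoint sampling only; no clinical follow-up or treatment rule is proposed.

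**SAP 5.3.1.** State that a telephone-only visit is a missing slide and PCR, not a negative one. List the subjects affected. Add a sensitivity analysis of time-to-onset with onset interval-censored between adjacent slides. Say whether elimination code 2090 applies to such a visit, since SAP Table 1 gives no interval for Visits 18–21.

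**Cost.** One sentence in the protocol; a short paragraph, one listing and one sensitivity analysis in the SAP. For an uninfected subject, one visit shifts by a day (two for a Monday challenge), with no added visits and no weekend staff. The price is an occasional 3-day interval between slides.
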